5.3 Dietary restrictions

- Subjects will be asked to fast for approximately 8 hours overnight on certain days where blood samples will be collected to measure various biomarkers and will be asked to fast at least 3-4 hours before MRI procedures as described in the SOM.
- Patients should maintain their usual physical activity and dietary habit and can drink water *ad libitum* to ensure adequate hydration during the study.
- Patients may reduce their carbohydrate intake in order to alleviate diarrhea, the primary adverse events associated with LIK066 administration with meals that contain high percentage of carbohydrate.
- To keep the dietary intake as consistent as possible, patients participating in this study will be counseled regarding appropriate exercise and diet per local standards, e.g. instruction to carefully adhere to American Heart Association (AHA) diet or equivalent if there is a country specific recommended diet.

5.4 Other restrictions

No initiation of strenuous physical exercise (e.g. weight training, aerobics, football) until after Study Completion evaluation.

6 Treatment

6.1 Study treatment

The study treatment includes once a day administration of either LIK066 (150mg) OR LIK066 (30mg) OR placebo for 12 weeks. Details on the requirements for storage and management of study treatment, and instructions to be followed for subject numbering, prescribing/dispensing and taking study treatment are outlined in the Site Operations Manual.

6.1.1 Investigational treatment and control drug(s)

The investigational drug, LIK066 and matching placebo, will be prepared by Novartis and supplied to the Investigator site as double blinded patient packs and will be dispensed based on the IVRS. Study treatments are defined as:

- 50 mg LIK066 tablets
- 10 mg LIK066 tablets
- Matching placebo tablets

6.1.2 Additional study treatment

No additional treatment beyond investigational drug and control drug are included in this trial.

6.2 Treatment arms

Initially patients will be assigned to one of the following two treatments (A or B) in a ratio of 2:1. Study treatments are defined as:

A: LIK066 150 mg

B: Matching placebo

A third, 30 mg qd arm (C) will be initiated after 33 patients have been enrolled in the initial two arm portion of the study. The randomization will change to a 2:4:1 ratio (150 mg: 30 mg: placebo) to maintain a 2:2:1 ratio across the three arms (150 mg:30 mg: placebo) at study end.

6.3 Treatment assignment and randomization

Randomized treatment will be assigned to individual patients by way of a randomization number. Randomization numbers will be assigned in ascending, sequential order to eligible patients via an IRT system (see Site Operations Manual for details).

The randomization number is only used to identify which treatment the patient has been randomized to receive. The Patient number assigned to a patient at screening remains the unique identifier for the patient throughout the study. For information on patient numbering, please see 'Patient numbering' section in the Site Operations Manual.

The randomization numbers will be generated using the following procedure to ensure that treatment assignment is unbiased and concealed from subjects and investigator staff. A subject randomization list will be produced by the IRT provider using a validated system that automates the random assignment of subject numbers to randomization numbers. These randomization numbers are linked to the different treatment arms, which in turn are linked to medication numbers. A separate medication list will be produced by or under the responsibility of Novartis Drug Supply Management using a validated system that automates the random assignment of medication numbers to packs containing the investigational drug.

Commercially Confidential Information

Commercially Confidential Information

6.4 Treatment blinding

This is a patient and investigator-blinded study. Patients and investigators will remain blinded to study treatment throughout the study, except where indicated below.

Drug product will be supplied as a double blinded patient packs and the identity of the treatments will be concealed by the use of study drugs that are all identical in packaging, labeling, schedule of administration, appearance, and odor.

Site staff

All site staff (including study investigator and study nurse) will be blinded to study treatment throughout the study.

Unblinding a single patient at site for safety reasons (necessary for patient management) will occur via an emergency system in place at the site (see [Section 6.7](#)).

Sponsor staff

The sponsor will remain unblinded to the treatment assignment of all patients to allow for continuous unblinded safety monitoring throughout the study.

Sponsor clinical staff are required to assist in the management and re-supply of investigational drug product. These individuals are not provided with randomization lists directly but may be unblinded through communication of drug re-supply needs via the IRT system.

The clinical trial team is allowed to share unblinded results with other sponsor staff (e.g. decision boards) as required for internal decision making on the study or the project while the study is ongoing.

Table 6-3 Blinding levels

Commercially Confidential Information

6.5 Treating the subject

LIK066 will be administered to the subject via the oral route. Patients will be provided with a supply of study medication to self administer once daily for 12 weeks (Day 2 to Day 84) before lunch. See the Site Operations Manual for further details.

Sponsor qualified medical personnel will be readily available to advise on trial related medical questions or problems.

6.6 Permitted dose adjustments and interruptions of study treatment

Investigational treatment dose adjustments and/or interruptions are not permitted.

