7.2 Discontinuation of study treatment

Discontinuation of study treatment for a patient occurs when study treatment is stopped earlier than the protocol planned duration. Discontinuation of study treatment can be decided by either the subject or the investigator.

Study treatment must be discontinued under the following circumstances:

- Patient decision - patients may choose to discontinue study treatment for any reason at any time.
- The investigator believes that continuation would negatively impact the safety of the patient or the risk/benefit ratio of trial participation.
- Any protocol deviation that results in a significant risk to the patient's safety
- Pregnancy (see [Section 8.6](#) (Safety) and [Section 9.6](#) (Pregnancy reporting))
- Discontinuation may be considered when patients have to be treated by prohibited medications on a case by case basis.

- Use of prohibited treatment as per recommendations in [Table 5-1](#)
- Hypersensitivity (CTCAE grade 2 or higher) reaction to LIK066 requiring intervention.
- Clinically significant diarrhea, suspected to be related to the study drug and not responsive to recommended management per SOM that may put the patient at risk (identified by investigator after consultation with the sponsor)
- Symptomatic orthostasis confirmed by repeated orthostatic blood pressure changes (more than a 20 mmHg drop in systolic or 10 mmHg drop in diastolic blood pressure and increase in heart rate >20 bpm (compared to sitting results) when blood pressure and pulse are taken after at least 3 minutes (standing)
- Clinically significant urinary tract or genitourinary infections, at the discretion of the investigator and consultation with the sponsor
- Clinically symptomatic hypoglycemia confirmed by repeated blood glucose levels (<56 mg/dL)
- Ketoacidosis (symptoms of ketoacidosis include nausea, vomiting, abdominal pain, unusual tiredness and trouble breathing) confirmed by blood pH and ketones.
- For ALT, AST, total bilirubin and/or alkaline phosphatase elevations mandating study treatment discontinuations, please refer to [Section 9.3](#) and [Table 9-1](#) and [Table 9-2](#) for further instructions and monitoring. Of note, ALT and AST are abnormal at baseline in this study. Thus only elevation to >2X of the baseline value will trigger events listed in [Section 9.3](#).
- Adverse events, abnormal laboratory values or abnormal test result that indicate a safety risk to the patient, in the opinion of the investigator

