Dose administration			X ¹⁴												
---------------------	--	--	-----------------	--	--	--	--	--	--	--	--	--	--	--	--

Commercially Confidential Information

MRI ¹⁶		X											X	X ¹⁷	
Comments	As required														
Concomitant therapies	X ¹⁸														
Study completion information														X	
Adverse Events	As required														X
Serious Adverse Events	As required														X

¹ Visit structure given for internal programming purpose only

² If a patient withdraws from the study, or if study medication is discontinued for any reason, the patient should be scheduled for a subsequent visit at which time all assessments at the EOS visit should be performed.

³ All assessments to be performed pre-dose

⁴ Informed consent must be provided by all patients before any screening procedures are performed. Commercially Confidential Information

Commercially Confidential Information

⁶ Serum pregnancy tests will be performed at Screening and end of study; urine tests may be used at other timepoints.

⁷ Blood pressure and pulse rate will be measured in a sitting position unless otherwise noted.

⁸ Measured in sitting and standing positions to assess orthostatic hypotension.

Commercially Confidential Information

¹⁰ Coagulation panel includes PT/INR and aPTT

Commercially Confidential Information

¹⁴ Patients will be provided with a supply of study medication to self administer once daily for 12 weeks (Day 2 to Day 84). Patients should bring all used and unused medications, and diaries, to each visit.

Commercially Confidential Information

¹⁶ MRI of abdomen and liver in all subjects. Quantification of liver fat will be performed on all subjects;

Commercially Confidential Information

¹⁷ Assessment is only to be performed at EOS if a patient withdraws from the study, or discontinues study treatment early for any reason.

¹⁸ A thorough review of any concomitant medications (including medication name, dose, unit, frequency, and route) should be performed at every visit.

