8.6.7 Pregnancy and assessments of fertility

Pregnancy Testing

All pre-menopausal women who are not surgically sterile will have pregnancy testing. See the [Assessment schedule \(Section 8.1\)](#), for timing of the protocol required pregnancy testing; additional pregnancy testing may be performed to meet local requirements*. A positive urine pregnancy test requires immediate interruption of study treatment until serum β -hCG is performed and found to be negative.

*Additional pregnancy testing might be performed if requested per local requirements.

Refer to [Section 9.6](#) for details on Reporting Pregnancy.

Assessments of Fertility

Refer to [Section 4.2](#) for criteria to determine women that are not of child bearing potential.

Medical documentation of oophorectomy, hysterectomy, or tubal ligation must be retained as source. Subsequent hormone level assessment to confirm the woman is not of child bearing potential must also be available as source documentation in the following cases:

- surgical bilateral oophorectomy without a hysterectomy
- reported 12 months of natural (spontaneous) amenorrhea with an appropriate clinical profile.

In the absence of the above medical documentation, FSH testing will be required.

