9.4 Renal safety monitoring

9.4.1 Renal safety monitoring

Every renal laboratory trigger or renal event must be followed up by the investigator or designated personnel at the trial site. Recommended actions and follow-up assessments are listed in [Table 9-4](#) and [Table 9-5](#), respectively.

Table 9-4 Specific Renal Alert Criteria and Actions

Renal Event	Actions
Serum creatinine increase 25 – 49% compared to baseline	Confirm 25% increase after 24-48h Follow up within 2-5 days
Serum creatinine increase > 50 % compared to baseline	Confirm > 50 % within 24-48 hours after receipt of the abnormal value If confirmation of abnormal value is not possible in this timeframe study drug must be withheld until further evaluation is possible Consider drug interruption Consider patient hospitalization / specialized treatment
Albumin- or Protein-creatinine ratio increase \geq 2-fold compared to screening or baseline levels whichever is higher	Confirm value after 24-48h Perform urine microscopy Consider drug interruption / discontinuation
New onset dipstick proteinuria \geq 3+	
Protein-creatinine ratio (PCR) \geq 1000 mg/g or \geq 100 mg/mmol	
New onset dipstick glucosuria \geq 1+ not due to diabetes	Blood glucose (fasting) Perform serum creatinine, ACR
New onset dipstick hematuria not due to trauma	Urine sediment microscopy Perform serum creatinine, ACR

Additional specialized assessments are available to assess renal function or renal pathology. (Note: In exceptional cases when a nephrologist considers a renal biopsy, it is strongly recommended to make specimen slides available for evaluation by Novartis to potentially identify project-wide patterns of nephrotoxicity.)

Whenever a renal event is identified, a detailed patient history and examination are indicated to identify, document and potentially eliminate risk factors that may have initiated or contributed to the event:

- Blood pressure assessment (after 5 min rest, with an appropriate cuff size)
- Signs and symptoms such as fever, headache, shortness of breath, back or abdominal pain, dysuria, hematuria, dependent or periorbital edema
- Changes in blood pressure, body weight, fluid intake, voiding pattern, or urine output
- Concomitant events or procedures such as trauma, surgical procedures, cardiac or hepatic failure, contrast media or other known nephrotoxin administration, or other potential causes of renal dysfunction, e.g., dehydration, hemorrhage, tumor lysis

Table 9-5 Follow-up of renal events

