9.8.3 Orthostatic hypotension

Because orthostatic hypotension is a potential risk of LIK066 treatment, orthostatic blood pressure readings will be recorded throughout the study as shown in the [Assessment schedule](#).

Any patient with clinically significant symptomatic orthostasis (more than 20 mmHg drop in systolic or 10 mmHg drop in diastolic blood pressure and increase in heart rate >20 bpm) will have the study treatment placed on hold. In addition, individuals with orthostasis will be treated with volume replacement according to standard of care (refer to [Section 7.2](#) (Discontinuation of study treatment)).

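### Section 6.6 bans every treatment interruption, yet 8.6.7, Table 9-4 and 9.8.3 order temporary holds; and confirmed hypoglycemia is a mandatory stop in 7.2 but an optional one in 9.8.2

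*Protocol*

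**What the plan says.** Section 6.6 of the protocol is a single sentence: "Investigational treatment dose adjustments and/or interruptions are not permitted". It names no exception and refers to no other section.

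Three later places order treatment to be paused:

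- Section 8.6.7: "A positive urine pregnancy test requires immediate interruption of study treatment until serum" testing gives a negative result. Urine testing is foreseen during treatment; footnote 6 of Table 8-1 reads "Serum pregnancy tests will be performed at Screening and end of study; urine tests may be used at other timepoints".
- Section 9.4.1, Table 9-4, for a serum creatinine rise above 50% from baseline: if the value cannot be confirmed in 24 to 48 hours, "study drug must be withheld until further evaluation is possible". The text before the table is softer: "Recommended actions and follow-up assessments are listed in" the two renal tables.
- Section 9.8.3: a patient with clinically significant symptomatic orthostasis "will have the study treatment placed on hold", with a reference to section 7.2. The list of mandatory stops in 7.2 includes "Symptomatic orthostasis confirmed by repeated orthostatic blood pressure changes". Standing blood pressure is a planned assessment (Table 8-1, footnote 8: "Measured in sitting and standing positions to assess orthostatic hypotension").

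Section 9.3, Table 9-2 and other entries in Table 9-4 only invite the site to consider an interruption.

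On hypoglycemia, section 7.2 puts symptomatic events confirmed by repeat glucose below 56 mg/dL under its *must* discontinue lead-in. Section 9.8.2, under a label that calls it a stopping rule, says that treatment *may* be discontinued at the same value.

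**The concern.** A site needs one answer to the question of whether drug may be paused. Section 6.6 says never, while the safety sections say that in certain events it has to be. Two consequences follow. A site that carries out the ordered hold has departed from 6.6 on its plain wording. A site that takes 6.6 literally, and rightly will not keep dosing, is left with permanent discontinuation for a patient who could have resumed, for example after a false-positive urine test.

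The hypoglycemia wording is a separate problem. Two passages give different instructions for one event at one threshold. In a multicenter trial, one site may stop a patient whom another would keep on drug. The event is foreseeable: Table 5-2 permits sulfonylureas and insulin, and 9.8.2 itself names patients on these drugs as possibly at increased risk.

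**Working it through.** No arithmetic applies. The check is to set each rule beside 6.6 and ask whether both can be followed as worded.

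| Trigger | Force of the instruction | Stated end of the pause | Compatible with 6.6 as worded? |
|---|---|---|---|
| Positive urine pregnancy test (8.6.7) | Required | Negative serum test | No: a temporary interruption with a defined end |
| Creatinine rise above 50%, not confirmable in 24 to 48 hours (Table 9-4) | *Must*, though 9.4.1 calls the table's actions recommended | When further evaluation is possible | No: a temporary withholding, conditional on failure to confirm |
| Clinically significant symptomatic orthostasis (9.8.3) | *Will* be held | None given; refers to 7.2 | No as worded, but reads best as a step before the 7.2 stop |
| Confirmed liver laboratory trigger (9.3); possible liver toxicity (Table 9-2); other Table 9-4 entries | *Consider* | None given | Not forced: the site can decline, but 6.6 leaves it no permission to accept |

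The first two rows are plain hold-then-resume rules. The third is weaker. Sections 9.8.3 and 7.2 use the same thresholds (a systolic fall of more than 20 mmHg or a diastolic fall of 10 mmHg, with a pulse rise above 20 bpm), and 7.2 adds confirmation on repeat. The hold therefore most naturally covers the interval up to the repeat reading, although 9.8.3 does not say so. The fourth row is loose wording, not a contradiction.

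The same comparison for hypoglycemia:

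| | Section 7.2 | Section 9.8.2 |
|---|---|---|
| Event | Clinically symptomatic | Clinically symptomatic |
| Confirmation | Repeat glucose | Repeat measurement |
| Threshold | Below 56 mg/dL | Below 56 mg/dL |
| Action | Must discontinue | May discontinue |

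Event, confirmation and threshold agree; only the action differs. Both passages are visible, and both are specific rules, so the usual principle that the specific governs the general does not choose between them.

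**The case against.** The strongest reply is that nobody would be harmed. Section 13.1 expects the investigator to take immediate safety action even where that is a deviation. Section 7.2 requires a stop when the investigator believes that continuing would harm the patient. Section 6.5 makes sponsor medical staff available for advice. A reader might infer from 6.6 that a site has to go on dosing after a positive pregnancy test or an unconfirmed creatinine rise; these provisions rule that out. What they leave standing is that compliance with 8.6.7 or Table 9-4 counts as a deviation from 6.6, and a protocol should not make its own ordered action a deviation. They also do not settle the hypoglycemia conflict.

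A second reply is that the *must* list in 7.2 is not uniformly mandatory: one bullet says that discontinuation may be considered, and another leaves the decision to the investigator in consultation with the sponsor. That is true, but the hypoglycemia bullet carries no such qualifier.

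A reader might also see a third contradiction in the two 7.2 bullets on prohibited medication, one case by case and one mandatory. They can be reconciled: one concerns a patient who needs such a drug, the other a patient who has used one, and 6.10 sends doubtful cases to the sponsor. At most, one bullet sits under the wrong lead-in.

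**Conclusion.** Both inconsistencies are real and should be corrected. Section 6.6 conflicts with two clear hold-then-resume rules and, more weakly, with the orthostasis hold. Confirmed symptomatic hypoglycemia has two different instructions at one threshold.

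The size is limited. The documents give no rates for any of these triggers, so the number of patients affected cannot be estimated. Counting the scheduled tests in Table 8-1 would not fill that gap, because a scheduled test is not an event: the renal hold also needs a rise above 50% and a failure to confirm it, and the orthostasis hold needs symptoms.

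A reader might infer that the inconsistency biases the ALT comparison, since section 11.1 removes patients from the PD set for deviations with a relevant impact on PD data. The documents do not support that. The visible text does not say whether an ordered hold would count as such a deviation, the analysis methods are redacted, and 7.2 asks patients who stop treatment to return for assessments where possible.

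The conclusion rests on the visible text. It assumes that neither the Site Operations Manual nor redacted material, including the block after the 7.2 list, already resolves these points.

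**What to change.** Two changes matter:

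- (a) Amend 6.6 so that adjustments and interruptions are not permitted except for the safety holds in 8.6.7, 9.3, 9.4.1 and 9.8.3. Including 9.3 gives the optional liver interruptions a clear basis. State in 9.8.3 that the hold lasts until the repeat measurement, with the 7.2 stop if orthostasis is confirmed.
- (b) In 9.8.2, make discontinuation mandatory for confirmed symptomatic hypoglycemia below 56 mg/dL, to match 7.2.

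Two minor tidy-ups can go in the same amendment. Move the case-by-case prohibited-medication bullet out of the 7.2 *must* list, and keep actual use as the mandatory stop. Align Table 8-1 footnote 17, which asks for an MRI after early discontinuation for any reason, with 8.5.5, which omits the end-of-treatment scan when treatment stops before Week 8.

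The cost is a few wording changes in one amendment, approved under section 13.1 by the sponsor, the IRB/IEC and, where required, health authorities. No patients, visits or scans are added.

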6.7 Emergency breaking of assigned treatment code

Emergency code breaks must only be undertaken when it is required to in order to treat the patient safely. Most often, study treatment discontinuation and knowledge of the possible treatment assignments are sufficient to treat a study patient who presents with an emergency condition. Emergency treatment code breaks are performed using the IRT. When the investigator contacts the system to break a treatment code for a patient, he/she must provide the requested patient identifying information and confirm the necessity to break the treatment code for the patient. The investigator will then receive details of the investigational drug treatment for the specified patient and a fax or email confirming this information. The system will automatically inform the study monitor for the site and the Study Team that the code has been broken.

It is the investigator's responsibility to ensure that there is a dependable procedure in place to allow access to the IRT at any time in case of emergency. The investigator will need to provide:

- protocol number
- study drug name (if available)
- patient number.

In addition, the investigator must inform the patient on how to contact his/her backup in cases of emergency when he/she is unavailable to ensure that un-blinding can be performed at any time.

An assessment will be done by the appropriate site personnel and sponsor after an emergency unblinding to assess whether or not study treatment should be discontinued for a given patient and whether the patient can continue in the study.

